**Table 3. Study Plan – Part B (Groups 3 to 8).**

Groups 3 to 8	Screening		Assessment Period												FU Visit	EOS Visit
	D-14 to D-2	D-1	Predose	H0	H1	H2	H3	H4	H5	H6	H7	H8	H10	H24		
	D1												D2	D8±1	D28±2	
SCREENING PROCEDURES																
Signature of the informed consent	X															
Medical history	X	X														
Prior medications	X	X														
Physical examination	X	X 												X 	X 	X 
Viral Serology	X															
Alcohol breath test & Urine Drug Screen	X	X														
Inclusion / exclusion criteria	X	X														
Randomisation				X												
24h Holter	X															
Hospitalisation																
Study treatment schedule				i.v. loading dose T0 to T15'												
Meals 		X										X			X	
SAFETY ASSESSMENTS																
Vital signs  (including BMI assessment at screening)	X	X	X	T0', T10', T20, T30, T40, T50'	X	X	X	X	X	X	X	X	X	X	X	X
ECG	X	X	X	T15'	X								X	X	X	
Telemetry 			X													
Haematology	X	X		T15'				X							X	
Coagulation	X	X		T15'				X							X	
Serum chemistry	X	X		T15'				X							X	
Urinalysis	X	X													X	
Infusion site assessment			X	T15' (6)	X	X		X		X		X			X	
Anti-LR12 antibody screening 			X												X	X
Pharmacokinetics 			X	T5', T15', T18', T30', T45'	X	X		X		X			T-15, T2', T4', T7', T15', T30	X		
Adverse Events	←														→	
Concomitant medication	←														→	

(1) Brief physical examination.

(2) Standard meals will be served at standard times. Meal at dismissal will be optional.

(3) Time of procedures is relative to the start of infusion.

(4) Tympanic temperature will be collected at pre-dose and at H8 only. Vital signs at H0 and H8 will be measured only in supine position.

(5) 12-Lead telemetry will be recorded from pre-dose to 10 h post-dose.

(6) The check of the local tolerability at H0 should be performed just after the loading infusion.

(7) PK sampling performed at the end of the 8 hours i.v. infusion will be as follows: 15 min before H8 (T-15'), then during 30 min after the end of the infusion as specified in the table. H0 timings refer to start of infusion.

---

(8) Should any subject develop ADA against LR12, they will be followed up for at least 3 months or until the antibody response is no longer detected.

## 8.2 Rules for Dose Escalation/Progression

A safety review committee (SRC) will review and assess at least the minimum required data from the previous group(s)/cohort(s) to make decisions on the dose(s) for the next dose levels/dosing regimen. The SRC will assess if any of the group or individual toxicity criteria are met and if the concerned AEs have a causal relationship with the IMP. If so, the SRC will take action in accordance with the rules stipulated in section [8.3](#).

There is an option to have ad-hoc SRC meetings to discuss urgent issues should the need arise.

### 8.2.1 Safety Review Committee

The SRC will consist of, as a minimum:

- Principal Investigator (RPL) or delegate
- INOTREM SA Medical Officer or delegate

Further internal or external experts such as a pharmacokineticist and/or a statistician, may be consulted by the SRC as necessary. Any additional information, if required will be included in the study operations manual (SOM).

### 8.2.2 Data Requirements

After each cohort the SRC will assess the minimum safety, tolerability and PK data required prior to dose escalation/progression (refer to dose escalation/progression section [8.2.4](#)). Prior to each SRC meeting, an interim safety report will be prepared for that group/cohort presenting the relevant safety and tolerability data. These will be signed by the PI and/or delegate. PK data will be provided separately by the analytical laboratory. As the initial data review will be blinded, there will be no link between the safety data and the PK data.

The following data will be required:

#### Safety:

- AEs
- Vital sign variables (temperature, blood pressure, heart rate)
- ECGs variables (12-lead ECG, telemetry and Holter)
- Clinical laboratory variables (haematology, coagulation, biochemistry, urinalysis)

#### PK

For availability of PK data, refer to section [8.2.4](#).

#### Additional data that may available at the time of report writing:

- Other relevant clinical tests conducted on a case-by-case basis

### 8.2.3 SRC Meeting

The SRC will determine dose escalations/progression according to the Clinical Study Protocol (CSP), anticipated doses, adaptive features and group toxicity rules. The decision will be signed by one of the Sponsor's representatives and by the PI or delegate. For logistical reasons, the signature of the Sponsor or Investigator may be communicated via email.

Initially the data will be reviewed blinded, but if the SRC consider it necessary due to a safety concern, either individual subjects or the entire cohort may be unblinded to enable their decision-making. Before breaking the code, the potential decisions and actions should be determined and documented.

The decision of the SRC on the next dose will be taken in consensus between the members of the SRC. If consensus cannot be reached, then the most cautious approach will proceed. The decisions and decision-making of the SRC on the next dose level will be documented and provided to the PI and Pharmacist prior to the next scheduled dosing day.

### 8.2.4 Dose Escalation/Progression

Dose escalation /progression is defined as either of the following:

1. Escalation to a higher exposure dosing regimen within Part A
2. Progression from Part A to Part B
3. Escalation to a higher exposure dosing regimen within Part B

Minimum data requirements for dose escalation/progression are:

1. **Escalation to a higher exposure dosing regimen between Part A (Groups 1 and 2 and optional groups)**  
A minimum of 24 hours post-dose (start of infusion) safety and tolerability data from one subject of the cohort with the next lower mean exposure level will be required.
2. **Progression from Part A to Part B**  
A minimum of 24 hours post-dose (start of infusion) safety and tolerability data from one subject on Part A's 10mg dose level will be required.
3. **Escalation to a higher exposure dosing regimen between Part B (Groups 3 to 8 and optional groups)**  
A minimum of 24 h post-last dose (start of infusion) safety, tolerability and PK data from a minimum of three subjects who have received the active compound from a previous cohort that was on the next lower dosing regimen (and hence, next lower exposure (mean and individual Cmax) levels of loading dose and mean and individual Cmax and Css inf of maintenance doses) will be required.

## 8.3 Toxicity Rules

### Group toxicity rules

For the purpose of this CSP, toxicity means clinically significant drug related adverse reaction(s).

For the purpose of this CSP the term 'dose escalation' means progression to a consecutive dose/dosing regimen or escalation to a dose/dosing regimen with an anticipated higher exposure in line with the dose progression/escalation rules and minimum data requirements.

For the purpose of this CSP the term 'suspension' means that no further IMP will be administered at the dose level/dosing regimen concerned and that further dose escalation/progression will be suspended. If a dose level/dosing regimen is suspended, an ad hoc SRC meeting will be held. Any resumption at the same or a higher exposure dose level/dosing regimen will require a substantial amendment which has been approved by the Competent Authority and the REC.

The group toxicity rules are described in Table 4.

**Table 4. Group Toxicity Rules.**

CTCAE Grade	Severity/ Seriousness	Reversibility	Number of Subjects Affected	Action	Effect on Dose Progression/Escalation
I	Mild	N/A	N/A		
II	Moderate	Showing signs of reversibility; i.e. event which shows signs of improvement in the judgment of investigator	≤2 subjects in different SOC	Next dose determined by SRC	N/A
			≤2 subjects in same SOC OR 3 subjects in different SOC*	Dose level may continue OR be extended AND Dose escalation on hold until results of continuation or extension are available	Following continuation or extension, dose escalation may proceed as per clinical study protocol
			≥3 subjects in same SOC OR ≥4 subjects in different SOC*	Dose level suspended	A lower (intermediate) dose level may be administered in the next cohort AND Dose continuation, extension, or escalation requires substantial amendment
			Showing no signs of reversibility		≥2 subjects*
III	Severe, not serious	Showing signs of reversibility; i.e. event which shows signs of improvement in the judgment of investigator	1 subject*	Dose level may continue OR be extended AND Dose escalation on hold until results of continuation or extension are available	Following continuation or expansion, dose escalation may proceed as per the clinical study protocol
			≥2 subjects*	Dose level suspended	A lower (intermediate) dose level may be administered in the next cohort AND Dose continuation, extension, or escalation requires substantial amendment
		Showing no signs of reversibility	≥1 subject		Severe, serious
		N/A			
IV	Life-threatening	N/A	≥1 subject	Study suspended	Study continuation requires substantial amendment
V	Fatal				

Abbreviations: AE=adverse event; N/A=not applicable; SOC=System Organ Class; SRC=Safety Review Committee

\* Within 2 weeks from each dose

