**Reason for Amendment:**

1. The purpose of this amendment is to adjust the maintenance dose increment between cohort 7 and cohort 8 to a factor of 2. The amendment describes the administration of a 6 mg/kg/h maintenance dose to cohort 8 in line with Adaptive Feature number 1, limit VII, Adaptive Features 2 and 3 Limits I and III.

The current approved protocol for the study MOT-C-104 (version 3.0 dated 13 May 2016) foresees an increment of 3 for the maintenance dose in all cohorts of Part B and progression to the maintenance dose of 9 mg/kg/h (over 7 hours and 45 minutes) in cohort 8.

Since the dose of 9 mg/kg/h is not planned for therapeutic use and was only foreseen to document the safety of the product, a reduced maintenance dose of 6 mg/kg/h is considered sufficient for documenting the safety of the product in healthy volunteers considering the currently available data. The Safety Review Committee agreed to escalate to the cohort 8 with an increment of 2 rather than 3 and thus give 6 mg/kg/h for 7 hours 45 minutes.

These changes will not affect the volunteers' safety.

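### In Table 4, one subject with a reversible Grade II reaction meets two rows: one leaves the next dose to the SRC, the other holds escalation

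*Combined protocol and SAP*

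**What the plan says.** Section 8.2 makes the table binding. If a toxicity criterion is met and the event is judged causally related, "the SRC will take action in accordance with the rules stipulated in section" 8.3.

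For Grade II reactions showing signs of reversibility, Table 4 has three rows:

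- **Row 1:** "≤2 subjects in different SOC". Action: "Next dose determined by SRC". The effect on escalation is given as not applicable.
- **Row 2:** "≤2 subjects in same SOC OR 3 subjects in different SOC" (asterisked: within 2 weeks of dosing). Action: "Dose level may continue OR be extended AND Dose escalation on hold until results of continuation or extension are available".
- **Row 3:** three or more subjects in the same SOC, or four or more in different SOCs. Action: the dose level is suspended.

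One subject with a reversible, non-serious Grade III reaction gets the same action as row 2, in the same words. That row names one subject explicitly.

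On how the SRC decides, section 8.2.3 adds: "If consensus cannot be reached, then the most cautious approach will proceed". For escalation within Part A, section 8.2.4 asks for at least 24 hours of "safety and tolerability data from one subject of the cohort with the next lower mean exposure level will be required".

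**The concern.** Rows 1 and 2 should divide the cases between them, but each sets its limit as at most two, so each takes in one affected subject. One person's reaction in one organ class fits either SOC description, and the two actions are incompatible: discretion over the next dose, or a mandatory hold.

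The row chosen decides whether the SRC may go to the next dose or must first wait for continuation or extension at the current one. Once a cohort is fully dosed, meeting the hold means extension. Table 1 (feature 8) caps that at 100% of the cohort: one more volunteer in a Part A group, up to four in a Part B group. In a first-in-human study, two readers could take opposite decisions from the same data and each cite Table 4.

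**Working it through.** **1. Which rows each pattern meets.** The inputs are the three reversible Grade II rows of Table 4, with one SOC per affected subject. The last column reads row 2 as exactly two subjects in the same SOC.

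| Affected subjects | Rows met as written | Rows met if row 2 says exactly two |
|---|---|---|
| 1 | Row 1 (SRC decides) and row 2 (hold) | Row 1 |
| 2, same SOC | Row 2 | Row 2 |
| 2, different SOCs | Row 1 | Row 1 |
| 3, same SOC | Row 3 (suspend) | Row 3 |
| 3, all different SOCs | Row 2 | Row 2 |
| 4, all different SOCs | Row 3 | Row 3 |
| 2 in one SOC + 1 in another | None | None |

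One subject is the only listed pattern that meets two rows. Changing the limit in row 2 removes the overlap and moves no other pattern.

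**2. Whether other text sets precedence.** Section 8.2 tells the SRC to apply the rules but does not rank the rows. Section 8.3 defines toxicity, dose escalation and suspension only. The footnote sets a 2-week window. Table 5 governs the individual's dosing, not group escalation. The consensus fallback in section 8.2.3 applies only when members disagree. Amendments 2, 3 and 4 leave Table 4 unchanged.

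**3. How often the case could arise.** In Part A as planned there is one subject per group, so any reversible Grade II reaction is this case. Each Part B cohort has 3 active subjects. The documents give no Grade II rate, so the per-subject rate p is assumed:

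- P(exactly 1) = 3p(1−p)²
- P(2 or more) = 3p²(1−p) + p³

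| Assumed p | P(exactly 1) | P(2 or more) |
|---|---|---|
| 0.02 | 0.058 | 0.001 |
| 0.05 | 0.135 | 0.007 |
| 0.10 | 0.243 | 0.028 |
| 0.20 | 0.384 | 0.104 |
| 0.30 | 0.441 | 0.216 |

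For example, at p = 0.10: 3 × 0.10 × 0.81 = 0.243. The ratio P(1)/P(2) is (1−p)/p, so one is a more likely count than two whenever p is below 0.5.

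**4. The dose steps that the hold would delay.** From Table 8 at 70 kg, total dose = loading dose + rate × 7.75 h × 70 kg. Group 8 is taken at 6 mg/kg/h, because under Amendment 4 "The Safety Review Committee agreed to escalate to the cohort 8 with an increment of 2 rather than 3": 350 + 6 × 7.75 × 70 = 3,605 mg.

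| Group | Total (mg) | Ratio to previous group |
|---|---|---|
| 1 | 1 | – |
| 2 | 10 | 10.0 |
| 3 | 51.3 | 5.1 |
| 4 | 124.2 | 2.4 |
| 5 | 302.8 | 2.4 |
| 6 | 892.5 | 2.9 |
| 7 | 1,977.5 | 2.2 |
| 8 | 3,605.0 | 1.8 |

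**The case against.** The best reply is that same and different SOC compare subjects with each other and so cannot describe a single subject. On that reading one subject meets neither row, and the general rule that the SRC decides the next dose applies, which is also row 1's outcome. A hold for one moderate reaction would, besides, erase the distinction from one severe reaction, so row 1 is the sensible reading. If SRC members disagreed, the cautious fallback would produce the hold. That leaves a unanimous SRC taking the reading that most people would prefer.

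Much of this stands as evidence of intent: row 1 probably is what was meant. It does not make the rule determinate. The relational reading leaves the simplest event with no row in a table the SRC must apply. The fallback does not say whether a unanimous SRC may escalate.

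Several limits on size also stand:

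- Row 1 permits escalation but does not compel it. The SRC could still extend the cohort or choose a lower dose, and Part B steps stay capped at 2.5-fold (loading) and 3.5-fold (maintenance) under either row.
- The dose ratios describe the planned scheme, not an effect of the ambiguity. The step from Group 2 to Group 3 compares a 15-minute infusion with an 8-hour one.
- The reaction rates are assumed. Because review is initially blinded, the SRC sees four Part B subjects, not three. If all four had the same rate, exactly one affected would have probability 0.171, 0.292, 0.410 and 0.412 at 5%, 10%, 20% and 30%.
- Amendment 2 added a second subject to Group 2, so the statement that any reversible Grade II reaction must be this case holds for Part A as planned, not for Group 2 as extended.

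**Conclusion.** The concern holds. As written, Table 4 prescribes two incompatible actions for one subject with a reversible Grade II reaction within 2 weeks of dosing, and no other text chooses between them. This follows from the wording alone and needs no assumption about rates. The assumed rates bear only on frequency: exactly one of 3 active subjects affected has probability 6% to 44% for p from 2% to 30%, against 0.1% to 22% for two or more. What turns on it is whether the next planned step, 1.8-fold to 10-fold in total dose, may be taken or must wait. SRC review still protects subjects, so this is a point that should be fixed, not a reason to judge the design unsafe.

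**What to change.** Edit two trigger cells in Table 4:

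- **Row 1:** one subject, or two subjects in different SOCs.
- **Row 2:** exactly two subjects in the same SOC, or three subjects in different SOCs.

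This keeps a single moderate reaction below the one-subject Grade III hold. If the sponsor does intend a hold for one Grade II subject, put that case in row 2 only and start row 1 at two subjects.

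The cost is a protocol amendment, with no added subjects or procedures. The wording of the toxicity rules is not among the adaptive features in Table 1, so the sponsor would need to decide whether the amendment is substantial and requires ethics committee approval. The pattern of two subjects in one SOC plus one in another, which meets no row on the reading used above, is a separate gap that this edit does not close; it could be settled in the same amendment.

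### Table 4's mandatory action weakens as severity rises: three subjects with reversible Grade II reactions in one SOC suspend the dose level, but two plus one with a reversible, non-serious Grade III only hold escalation.

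*Combined protocol and SAP*

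**What the plan says.** Section 8.3 and Table 4 set the group actions grade by grade, counting subjects with clinically significant drug-related reactions. The rows that matter here are those for reactions showing signs of reversibility.

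- **Grade II, suspend:** "≥3 subjects in same SOC OR ≥4 subjects in different SOC".
- **Grade II, hold:** "≤2 subjects in same SOC OR 3 subjects in different SOC".
- **Grade III, not serious:** one subject gives a hold, two or more give suspension.

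A hold has the same action text in both grades: "Dose level may continue OR be extended AND Dose escalation on hold until results of continuation or extension are available". For the single Grade III subject the table then states: "Following continuation or expansion, dose escalation may proceed as per the clinical study protocol".

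Suspension is much stronger. Section 8.3 defines it to mean that "no further IMP will be administered at the dose level/dosing regimen concerned", and Table 4 adds: "Dose continuation, extension, or escalation requires substantial amendment". A lower, intermediate dose stays available. Section 8.3 also says: "Any resumption at the same or a higher exposure dose level/dosing regimen will require a substantial amendment", with approval by the Competent Authority and the REC.

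Part B cohorts have three active subjects and one placebo subject. Section 8.2.2 says of the committee's data: "As the initial data review will be blinded, there will be no link between the safety data and the PK data". Table 1 allows a cohort to be extended by up to 100% and keeps Table 4 in force during the extension.

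**The concern.** A group stopping rule should never ask for less when one of the counted subjects does worse. Table 4 does. If three subjects in a cohort have reversible Grade II reactions in one SOC, the level is suspended. Make one of those reactions a reversible, non-serious Grade III and the Grade II count falls to two, the Grade III count is one, and both rows give only a hold.

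The group toxicity rules are the mandatory safeguard of a first-in-human escalation. In the affected pattern, more healthy volunteers may be dosed at the same level, and escalation may later proceed, without the approvals that three moderate reactions would have required. The case that matters most in a planned Part B cohort is the one in which every active subject has reacted.

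**Working it through.** The documents give no operating characteristics for this rule, so there is no stated figure to reproduce.

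**1. Table 4 as written (one SOC; all reactions reversible, Grade III non-serious; the stricter row applies)**

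| Subjects at Grade II | Subjects at Grade III | As written | If the Grade II suspension count means Grade II or worse |
|---|---|---|---|
| 3 | 0 | suspend | suspend |
| 2 | 1 | **hold** | suspend |
| 1 | 2 | suspend | suspend |
| 0 | 3 | suspend | suspend |
| 2 | 0 | hold | hold |
| 1 | 1 | hold | hold |

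Across different SOCs, four Grade II subjects suspend, but three plus one Grade III hold.

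**2. Search for reversals.** Every single change from Grade II to Grade III was checked for 3, 4, 6 and 8 subjects over up to four SOCs, reading the different-SOC count either as total subjects or as distinct SOCs. For 3 or 4 subjects the table as written weakens only from 3 or 4 Grade II subjects with no Grade III. With the pooled count there is no weakening in any case.

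**3. How often the pattern arises (assumed rates).** Let q be the probability that a subject has a Grade II or III reaction and s the share that are Grade III. Subjects are independent, and all reactions are in one SOC, reversible and non-serious.

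- Three active subjects: P(2 Grade II + 1 Grade III) = 3[q(1−s)]²(qs). At q = 0.2, s = 0.25: 3 × 0.15² × 0.05 = 0.0034.
- Four subjects, the placebo subject counted like an active one because review is blinded (upper bound): 12[q(1−s)]²(qs)(1−q). At q = 0.2, s = 0.25: 12 × 0.15² × 0.05 × 0.8 = 0.0108.

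| q (s = 0.25) | 3 active | 4 subjects, upper bound |
|---|---|---|
| 0.1 | 0.04% | 0.15% |
| 0.2 | 0.3% | 1.1% |
| 0.5 | 5.3% | 10.5% |

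At q = 0.2, a severe share of 0.1 or 0.5 gives 0.2% or 0.3% (three active) and 0.6% or 1.0% (four). The different-SOC version needs four reactors, so in a planned cohort it is zero unless the placebo subject counts; otherwise it is at most 4[q(1−s)]³(qs) = 0.07% at q = 0.2 and 2.6% at q = 0.5.

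**4. Given exactly three reactors in one SOC.** P(2+1) = 3(1−s)²s: 24% at s = 0.1, 42% at s = 0.25, 37.5% at s = 0.5.

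**5. Overall probability of suspension (one SOC, s = 0.25)**

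| Subjects | q | As written | Pooled count | If all reactions were moderate |
|---|---|---|---|---|
| 3 active | 0.1 | 0.23% | 0.27% | 0.10% |
| 3 active | 0.2 | 1.06% | 1.40% | 0.80% |
| 3 active | 0.5 | 9.57% | 14.84% | 12.50% |
| 4, upper bound | 0.1 | 0.52% | 0.67% | 0.37% |
| 4, upper bound | 0.2 | 2.60% | 3.68% | 2.72% |
| 4, upper bound | 0.5 | 23.05% | 33.59% | 31.25% |

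The table as written suspends less often than it would with purely moderate reactions only above q of about 0.31 (three active) or 0.18 (four). With s = 0.1 these crossovers are 0.11 and 0.06; with s = 0.5 they are 0.67 and 0.50.

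**6. Exposure after a 2+1 hold.** Four subjects plus a 100% extension is eight, six of them active. The pattern needs at least three dosed, so at most 8 − 3 = 5 more. Of these, 3 are active if all reactors were active, or 4 if one was on placebo. With three more active subjects, one further same-SOC Grade II or any Grade III suspends: 1 − (1−q)³ = 27%, 49% and 88% at q = 0.1, 0.2 and 0.5.

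**The case against.** The strongest reply is that the table is silent, not wrong: Grade II may have been meant as Grade II or higher, and on that reading the reversal disappears. That may be the intention, but neither the table nor the text says so, and Grade III has its own rows with its own counts. A committee following the text would hold.

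The second reply is that other safeguards remain. Escalation needs a satisfactory committee review of all safety data. Continuing the level is optional. Dosing after the sentinel needs acceptable tolerability (section 8.4.4), and a disagreement is settled by the more cautious choice (section 8.2.3). All this is true and limits the harm, but none of it makes suspension mandatory, and the tie-break does nothing if both minimum members read the table the same way.

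Third, the gap tends to close itself. After three of three active subjects have reacted, the unconditional extension figures are too low. With a uniform prior on the reaction rate, the posterior is Beta(4,1), and the chance of at least one more same-SOC reaction among three further active subjects is 1 − B(4,4)/B(4,1) = 1 − (1/140)/(1/4) = 97%. This stands, but the rule then stops only after another volunteer has reacted.

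Fourth, the size rests on assumed inputs and is small at low rates, where the table as written suspends more often overall than with purely moderate reactions. This too stands; the 42% applies only once exactly three subjects have reacted in one SOC. The five further subjects also require the fourth cohort member to be undosed; otherwise it is four.

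Finally, the search covered only changes from Grade II to Grade III among reversible, non-serious reactions. It says nothing about the rows for reactions showing no reversal or for serious reactions.

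**Conclusion.** The point holds. Following Table 4 as written, a worse pattern of reactions leads to a weaker mandatory action: 3+0 suspends and 2+1 holds in one SOC, and 4+0 suspends and 3+1 holds across SOCs. This conclusion needs no assumed rate. It does need the literal reading, in which the Grade II rows count only Grade II.

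The practical size is modest. The pattern is uncommon at 10% to 20% reacting and reaches about 5% (three active) to 10.5% (four, upper bound) only at 50% reacting with a quarter severe. What is lost is a mandatory stop at the same dose level, with the Competent Authority and REC approval that goes with it. The table does not allow escalation straight through the toxicity. A correction is worth making because this is the protocol's binding safety rule.

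**What to change.** Add one footnote to the Grade II suspension row of Table 4: the count in "≥3 subjects in same SOC OR ≥4 subjects in different SOC" is of subjects with a drug-related reaction of Grade II or worse. The Grade III rows continue to apply in their own right and the other rows stay as they are, so a single Grade II subject is handled as now. The footnote should also say whether a Grade II reaction showing no sign of reversal counts. The decision is for the sponsor and the Safety Review Committee.

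The cost is somewhat more frequent suspension, and so more amendments: +0.3 percentage points at 20% reacting and +5.3 at 50% (three active, a quarter severe), or at most +1.1 and +10.5 for four subjects. Every changed pattern moves from hold to suspend.

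Table 1 has no adaptive feature for changing a stopping rule, and Amendment 4 was classed as non-substantial because it applied approved adaptive features. A mid-study change may therefore need a substantial amendment. By Amendment 4 the committee had agreed to move to Group 8, the last planned cohort, so from then on the benefit is confined to that cohort and any optional or extended ones.
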